3.1. PRIMARY OUTCOME

The primary outcome is the oxygenation response, as determined by change in OI (or OSI if no arterial blood gas is available) at 24h after initiation of study drug. In patients that require ECMO or die prior to completion of 24h from the initiation of the study drug, the last OI (or OSI, if no arterial blood gas is available) prior to initiation of ECMO or death will be used for analysis. A difference in OI of 4 points in mean change from baseline OI at 24 h between experimental and control groups will be considered significant (OI increased by 4 ± 14.8 in the control group and decreased by 2.7 ± 23.4 following iNO in the CDH NINOS study (1997). In the Patel study, following milrinone infusion, OI decreased by 2.7 ± 1.7 from baseline by 12-24 h and 5.5 ± 3.2 by 48-72 h; the mean change in OI of both these time points is a decrease by 4.1 ± 1.5 (Patel 2012)). This outcome will be used for sample size calculation. Although a decrease in OI by 4 points may not be clinically significant, this number is based on the only published case series showing the use of milrinone in CDH. In patients without an arterial line (or if the line is lost), oxygen saturation index (OSI) will be calculated using a preductal oximeter. (Rawat, Chandrasekharan et al. 2015)

Oxygenation index (OI) = Mean airway pressure (cm H₂O) x FIO₂ x 100 ÷ PaO₂ (mm Hg)

Oxygen saturation index (OSI) = Mean airway pressure (cm H₂O) x FIO₂ x 100 ÷ SpO₂ (%)

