3.2. SECONDARY OUTCOMES

- (i) Oxygenation response at 24 h after initiation of study drug assigning a minimum OI of 40 or OSI of 20 (if no arterial blood gas is available) for subjects that need ECMO or die after initiation of study drug infusion but prior to 24h of study-drug infusion. In this analysis if the patient's OI is 30 (or OSI of 15) and is cannulated for ECMO due to hemodynamic instability, he/she will be assigned an OI of 40 (or OSI of 20). However, if the OI prior to ECMO is 47 (i.e., > 40), the higher number (47) will be used for analysis of this secondary outcome.
- (ii) Oxygenation index at 48 and 72 h after initiation of study drug (or OI/OSI at the time of initiation of ECMO or immediately prior to death, for infants placed on ECMO or died before these time points),
- (iii) Change in echocardiographic findings – velocity of tricuspid regurgitation, left ventricular ejection fraction, position of the interventricular septum and direction of shunt at the PDA and PFO level – prior to and 24-72h after starting the study

medication. This outcome will be available only for those infants who have a pre-study drug echocardiogram and a second echocardiogram between 24-72 h after initiation of study drug. These data will be extracted from echocardiograms performed for clinical indications.

- (iv) Vasoactive Inotrope score and systemic blood pressure
- (v) Area under the curve for inspired oxygen after initiation of the study drug over the first 72 hours of study-drug infusion (or prior to ECMO or death, whichever is earlier) (Note: inspired oxygen and ventilator data from 4 time points per day – every 6 hours will be recorded to calculate area under the curve),
- (vi) If subsequent to the study drug, any additional inotrope or pulmonary vasodilator is used (such as iNO), we will evaluate the oxygenation response to these agents. If inotropes or vasodilators were used prior to the initiation of study drug, similar values will be recorded. The OI (or OSI) and $\text{PaO}_2/\text{FiO}_2$ ratio prior to and after initiation of the inotrope / vasodilator are recorded (these data are recorded at 6 hour intervals; the date and time of initiation of individual inotropes and vasodilators is recorded). The change in OI (or OSI) and $\text{PaO}_2/\text{FiO}_2$ ratio in response to these agents is evaluated as a continuous variable and arbitrarily classified into responders, partial responders and non-responders similar to prior trials (1997, 1997).

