 - Midline shift secondary to mass effect from an intracranial hemorrhage
- thrombocytopenia (platelet count < 80,000/mm³) despite blood product administration on the most recent blood draw prior to randomization
- coagulopathy (PT INR > 1.7) despite blood product administration on the most recent blood draw (if checked – there is no reason to check PT for the purpose of this study)
- aneuploidy associated with short life span (such as trisomy 13 or 18) will not be included in the study (infants with trisomy 21 can be included in the study)

- use of milrinone infusion prior to randomization (the use of other inhaled pulmonary vasodilators such as iNO, inhaled epoprosternal, inhaled Treprostinal, inhaled PGE1 and oral such as endothelin receptor antagonists is permitted – Note: it is unlikely to be on oral pulmonary vasodilators early in the course of CDH)
- ongoing therapy with parenteral (intravenous or subcutaneous) pulmonary vasodilators such as IV/SQ prostacyclin analogs (Epoprostenol – Flolan® or Treprostinal – Remodulin®) or IV phosphodiesterase 5 inhibitors (sildenafil – Revatio®) at the time of randomization. Administration of IPGE1 is not an exclusion criteria. In addition, initiation of therapy with these two classes of parenteral medications (except IPGE1) during the first 24 hours of study drug initiation is not permitted and will be considered a protocol deviation. The risk of systemic hypotension is high during the first 24 hours of study-drug (milrinone) infusion and hence parenteral administration of other pulmonary vasodilators is avoided to minimize risk of hypotension.
- Subjects already on ECMO or patients who are being actively considered for ECMO by the neonatal or surgical team
- Infants with hypoxic-ischemic encephalopathy (HIE) undergoing therapeutic hypothermia
- attending (neonatal, critical care or surgical) refusal for participation in the trial (including concern about presence of hemodynamic instability)

Note:

1. A clotting profile evaluation is not required prior to enrollment. However, a cranial ultrasound (covered by the study budget) must be obtained either prior to initiation of study drug or within 4 hours of initiation of study drug. Not obtaining a cranial ultrasound within this time period will be considered a protocol deviation.

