Criteria for re-initiation of study drug:

After the patient has met criteria for study drug discontinuation once (due to improvement in oxygenation and meeting OI criteria, or due to side effects such as severe hypotension, intracranial bleeding or renal dysfunction), study drug is discontinued and cannot be reinitiated even if the indication for initial discontinuation is resolved (for e.g., OI exceeds 10 after cessation of study drug or hypotension is resolved and blood pressure is normal etc.,). The clinical team may start open-label milrinone.

During the post-study drug infusion period, data regarding open-label milrinone use, pressor use, and vasodilator use will be recorded for 24 hours after cessation of study-drug.

Fluid intake:

- (i) As systemic hypotension and fluid bolus administration are common in patients with CDH and PPHN, it is important to record daily fluid intake.
- (ii) Total fluid intake (including maintenance fluids/TPN, flushes, medications, boluses and blood products) will be recorded for three 24-hour periods as entered in the nursing notes/EMR (please see MOP for details).

Clinical criteria for ECMO:

The decision to place an infant with CDH on ECMO is ***entirely up to the clinical team***. Many centers prefer to use ECMO for preoperative stabilization. The following general guidelines are provided as criteria for ECMO (Reiss, Schaible et al. 2010) (Snoek, Reiss et al. 2016):

- (i) Oxygenation index is consistently ≥ 40 for at least 3 h and/or
- (ii) Inability to maintain preductal saturations $> 85\%$ or postductal saturations $> 70\%$ and/or
- (iii) Increased PaCO_2 and respiratory acidosis with $\text{pH} < 7.15$ despite optimization of ventilator management and/or
- (iv) $\text{PIP} > 28 \text{ cm H}_2\text{O}$ or mean airway pressure $> 17 \text{ cm H}_2\text{O}$ is required to achieve saturations $> 85\%$ and $\text{PaCO}_2 < 65 \text{ mmHg}$ and/or
- (v) Inadequate oxygen delivery with metabolic acidosis as measured by elevated lactate $\geq 5 \text{ mM/L}$ and $\text{pH} < 7.15$ and/or
- (vi) Systemic hypotension (mean blood pressure $< 30 \text{ mmHg}$), resistant to fluid and inotropic support, resulting in hypoperfusion and/or oliguria (urine output $< 0.5 \text{ mL/kg/h}$) for at least 12-24h

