5.1 SAMPLE SIZE AND POWER ESTIMATES

Sample Size: In the case series describing the effect of milrinone among neonates with CDH, baseline OI (mean \pm SD) was 10.6 ± 5.6 , and improved to 7.9 ± 6.2 and 5.1 ± 2.6 at 12-24 h and at 48-72 h, respectively (Patel 2012). Assuming that children receiving placebo will have no additional change in OI (mean change in OI = 0 at 24 hours), that children receiving milrinone will improve to a mean OI of 6.0 (a mean change in OI of 4.6) at 24 hours, and that the standard deviation of the change from baseline OI at 24 hours in each group is 6.2, 33 subjects in the control group and 33 subjects in the milrinone group would have 84% power to detect this difference with a two-sided alpha of 0.05 (note that 6.2 is a conservative standard deviation estimate, as data from the Patel et al study indicate that the standard deviation for change from baseline in OI at 24 hours may be as low as 1.5). Phrased differently, if both the control and treatment OI's were to change, for any given difference in OI, the sample size would be sufficient to detect an effect size of 0.7 with a power of 84%. The sample size will be sufficient to provide estimates of adverse event rates in the treatment group. The following table provides the 95% confidence intervals for observed adverse event rates varying from 6% to 49% for a sample size of 33 subjects.

Table 8. Confidence Intervals for Observed adverse event rates.

Point estimate	0.06	0.09	0.21	0.30	0.39	0.49
95% CI	(0.007, 0.2)	(0.02, 0.24)	(0.09, 0.39)	(0.16, 0.49)	(0.23, 0.59)	(0.31, 0.66)

Within the NRN centers, approximately 36% of neonates with CDH who are \geq 36 weeks PMA require ECMO. In a selective population (isolated CDH with OI \geq 10), we estimate that the risk of ECMO or death prior to discharge (or by day 120) will be approximately 40%. A sample size of 33 in the placebo arm would provide a 95% confidence interval for this estimate of (26%, 58%). The precision of estimates for outcome rates in the treatment group can be seen in table 8.

Limitations:

- (a) This study is not powered to compare rates of the outcome of death or ECMO between groups. To detect a reduction of 10% (from 40% incidence of death/ECMO in control arm to 30% incidence in the milrinone arm), with a 1:1 ratio of treatment and control subjects, a power of 0.8 and an alpha value of 0.05, we would require 376 subjects in each arm.

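### Because infants who need ECMO or die before 24 h keep their last earlier OI, the primary outcome can favour milrinone while more milrinone infants fail early; a positive primary result should not stand alone

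*Combined protocol and SAP*

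**What the plan says.** Section 3.1, repeated in the synopsis, defines the primary outcome as the change in OI (or OSI) 24 h after study drug starts. It then covers early failures: "In patients that require ECMO or die prior to completion of 24h from the initiation of the study drug, the last OI" (or OSI) "prior to initiation of ECMO or death will be used for analysis". Neither 3.1 nor 5.4 limits how old that last value may be.

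Secondary outcome (i) in 3.2 analyses the same response "assigning a minimum OI of 40 or OSI of 20 (if no arterial blood gas is available) for subjects that need ECMO or die" before 24 h. Its worked example is the case at issue: if an infant at OI 30 is "cannulated for ECMO due to hemodynamic instability, he/she will be assigned an OI of 40".

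Section 5.4 tests the primary outcome with one linear model adjusted for HRF severity. It gives no term or sensitivity analysis for early failures, and no rule linking a conclusion of benefit to secondary (i) or to secondary (viii), survival without ECMO. Section 5.1 assumes that "children receiving placebo will have no additional change in OI".

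On the drug's risk, 4.1.2 states: "The risk of systemic hypotension is high during the first 24 hours of study-drug (milrinone) infusion". Section 4.2.5 leaves the ECMO decision to the clinical team. Its guideline criteria list resistant hypotension, acidosis and ventilator pressure separately from an OI of 40 or more.

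**The concern.** The last value before ECMO or death describes oxygenation up to the failure and gives no weight to the failure itself. No blood is drawn for research (4.2.5), and 3.2 describes oxygenation and ventilator data at 6-hour intervals. After a very early event the last value may therefore be at or near baseline. The change is then about 0, which is the mean that 5.1 assumes for placebo infants.

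The route matters because hypotension is the drug's named early risk, its high-risk period is the primary outcome's window, and it can lead to ECMO without first raising OI. Survival without ECMO is what the programme ultimately aims to improve (2.1). A favourable oxygenation result that coincides with more early ECMO or death could be read as short-term benefit when the reverse is true.

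**Working it through.** **Reproducing the plan's figure.** Section 5.1 gives 33 per arm, difference 4.6, SD 6.2, two-sided alpha 0.05 and 84% power. Effect size = 4.6/6.2 = 0.742. Noncentrality = 0.742 × √(33/2) = 3.01. The two-sample t-test with 64 degrees of freedom then has power 84.3%, which agrees.

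**Single infants.** Each score is the change from baseline; negative means improved.

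| Baseline OI | Last OI before ECMO | Primary | Secondary (i) |
|---|---|---|---|
| 30 | 30 | 30 − 30 = 0 | 40 − 30 = +10 |
| 32 | 30 | 30 − 32 = −2 | 40 − 32 = +8 |
| 45 | 38 | 38 − 45 = −7 | 40 − 45 = −5 |

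The last row shows that the floor of 40 is also incomplete: this infant goes onto ECMO and still scores as improved.

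**Expected difference on the primary.** Let p_M and p_P be the shares failing before 24 h on milrinone and placebo, and d the failing infants' mean change to their last OI, equal in both arms. With an effect of −4.6 in infants who do not fail:

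difference = −4.6 × (1 − p_M) + d × (p_M − p_P).

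- 20% v 10%: −3.68 + 0.1d, which is −3.68, −2.68 and −1.68 at d = 0, +10 and +20.
- 30% v 10%: −3.22 + 0.2d, which is −3.22, −1.22 and +0.78.

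**Simulated chance of declaring benefit.** Inputs from 5.1: 33 per arm, SD 6.2, effect 4.6 in infants who do not fail. Assumed: the failure rates, d, and a baseline OI of 20 ± 8 with a floor of 10 (20 ± 8 is Table 6's figure for infants with OI of 10 or more at 6 h who survived without ECMO). The primary and secondary (i) were compared by t-test without the HRF adjustment. The worst-rank test is a Wilcoxon test with early failures ranked below everyone else.

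| Early failure, milrinone v placebo | d | Primary | Secondary (i) | Worst-rank |
|---|---|---|---|---|
| 20% v 10% | 0 | 65% | about 12% | about 26% |
| 20% v 10% | +5 | 46% | about 12% | about 26% |
| 20% v 10% | +10 | 29% | about 11% | about 26% |
| 20% v 10% | +20 | 11% | about 8% | about 26% |
| 30% v 10% | 0 | 52% | 1–2% | 6% |
| 30% v 10% | +10 | 9% | 1–2% | 6% |
| 30% v 10% | +20 | 1% | about 1% | 6% |

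Secondary (i) depends on the baseline, since a higher baseline leaves less room below 40. At 25 ± 12 and d = 0 it declares benefit in up to about 16% of trials at 20% v 10%.

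**A drug with no effect on OI.** Suppose 20% of placebo infants fail with last OI up by 20, while 30% of milrinone infants fail earlier with last OI unchanged. The expected difference is 0.3 × 0 − 0.2 × 20 = −4.0, and the primary declares benefit in about 47% of trials, against a nominal 2.5%. If the placebo failures rise by 10 instead, the rate is 21%.

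**Effect of a same-direction condition.** If a significant primary counts only when secondary (i) also favours milrinone in its point estimate, then at d = 0 the rate falls from 65% to 58% at 20% v 10%, and from 52–54% (across runs) to about 31% at 30% v 10%. With 10% failing in each arm, power at the planned effect goes from about 75% to 74%. Requiring significance on both would cut it to about 42%.

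**The case against.** The strongest reply is that the largest figures depend on failing infants' OI being unchanged, and the documents lean the other way. The first ECMO guideline criterion in 4.2.5 is an OI of at least 40 for 3 h. In Table 6, infants with OI of 10 or more at 6 h averaged 35 if they later had ECMO or died, against 20 if they did not (a cross-sectional contrast, not a change). Section 3.5 links hypotension to shunting and hypoxaemia, which raise OI. The hypotension criterion for ECMO refers to hypoperfusion or oliguria over at least 12 to 24 h. Infants already severely hypotensive or being considered for ECMO are excluded. This stands: at +20 the primary declares benefit less often than the worst-rank test would. A 30% failure rate within 24 h is also extreme beside the 40% that 5.1 expects by discharge or day 120.

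A reader might infer that the primary cannot see haemodynamic harm at all, or that its result decides the trial and passes into the definitive study. The documents do not support either. Where hypotension worsens oxygenation, the last OI registers it. This is a pilot for feasibility, short-term efficacy and safety (2.1). Secondary (i) and (viii) are prespecified, severe hypotension is a DSMC trigger (5.5.3), no go/no-go rule rests on the oxygenation p-value, and the definitive trial's primary outcome is survival without ECMO (5.5.3.2).

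Nor do the documents force a worst-rank primary. ECMO is discretionary and 4.2.5 says many centres use it for preoperative stabilisation, so ranking every ECMO infant with the deaths would bring centre practice into the primary. It would also lower power from about 75% to 63% when 10% of each arm fail early with OI unchanged.

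What the reply does not remove is that the primary's answer moves from 65% to 11% according to how ECMO was triggered, which the plan does not control. Section 5.1 also says the study is not powered to compare death or ECMO between arms, so secondary (viii) cannot be relied on to expose the discrepancy.

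**Conclusion.** The concern holds in conditional form. The rule in 3.1 allows the primary to favour milrinone while more milrinone infants need ECMO or die before 24 h, when those events are haemodynamic or come before OI has risen. At assumed failure of 20% v 10% the primary declares benefit in about 65% of trials if failing infants' last OI is unchanged, 29% at +10 and 11% at +20. The range is the finding; the top figure alone is not. It rests on the plan's own sample size, effect and SD, and on assumed early-failure rates, last-OI changes and baseline OI, with failing infants given the same baseline distribution as the rest. The case is for limiting what a positive primary result may conclude, not for replacing the primary test.

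**What to change.** Keep the last-value linear model as the primary analysis. In 3.1 and 5.4:

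1. State that it estimates oxygenation only while alive and off ECMO.
2. State that benefit at 24 h is not concluded from it alone: secondary (i) must point the same way, and the number with ECMO or death before 24 h is reported by arm beside it.
3. Add, as a sensitivity analysis, a rank test stratified by HRF severity in which infants with ECMO or death before 24 h rank below all others.

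The cost is wording, one extra analysis and about one point of power under the direction-only condition. No new data are needed. Because that condition reduces the problem without removing it, the early-failure counts must be read with it. Requiring significance on both outcomes is not advised in a trial of 66 infants, given the loss of power.

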3.2. SECONDARY OUTCOMES

- (i) Oxygenation response at 24 h after initiation of study drug assigning a minimum OI of 40 or OSI of 20 (if no arterial blood gas is available) for subjects that need ECMO or die after initiation of study drug infusion but prior to 24h of study-drug infusion. In this analysis if the patient's OI is 30 (or OSI of 15) and is cannulated for ECMO due to hemodynamic instability, he/she will be assigned an OI of 40 (or OSI of 20). However, if the OI prior to ECMO is 47 (i.e., > 40), the higher number (47) will be used for analysis of this secondary outcome.
- (ii) Oxygenation index at 48 and 72 h after initiation of study drug (or OI/OSI at the time of initiation of ECMO or immediately prior to death, for infants placed on ECMO or died before these time points),
- (iii) Change in echocardiographic findings – velocity of tricuspid regurgitation, left ventricular ejection fraction, position of the interventricular septum and direction of shunt at the PDA and PFO level – prior to and 24-72h after starting the study

medication. This outcome will be available only for those infants who have a pre-study drug echocardiogram and a second echocardiogram between 24-72 h after initiation of study drug. These data will be extracted from echocardiograms performed for clinical indications.

- (iv) Vasoactive Inotrope score and systemic blood pressure
- (v) Area under the curve for inspired oxygen after initiation of the study drug over the first 72 hours of study-drug infusion (or prior to ECMO or death, whichever is earlier) (Note: inspired oxygen and ventilator data from 4 time points per day – every 6 hours will be recorded to calculate area under the curve),
- (vi) If subsequent to the study drug, any additional inotrope or pulmonary vasodilator is used (such as iNO), we will evaluate the oxygenation response to these agents. If inotropes or vasodilators were used prior to the initiation of study drug, similar values will be recorded. The OI (or OSI) and $\text{PaO}_2/\text{FiO}_2$ ratio prior to and after initiation of the inotrope / vasodilator are recorded (these data are recorded at 6 hour intervals; the date and time of initiation of individual inotropes and vasodilators is recorded). The change in OI (or OSI) and $\text{PaO}_2/\text{FiO}_2$ ratio in response to these agents is evaluated as a continuous variable and arbitrarily classified into responders, partial responders and non-responders similar to prior trials (1997, 1997).
 - a. complete response is defined as an increase in $\text{PaO}_2/\text{FiO}_2$ ratio $> 20 \text{ mmHg}$ from baseline,
 - b. partial response is an increase in $\text{PaO}_2/\text{FiO}_2$ ratio of 10 to 20 mmHg from baseline,
 - c. no response is defined as an increase of $< 10 \text{ mmHg}$ (or a decrease) in $\text{PaO}_2/\text{FiO}_2$ ratio from baseline,
 - d. the site of sampling (preductal vs. postductal) is also recorded. (Gien and Kinsella 2016); right radial and ulnar arterial lines/sticks will be considered preductal; Left radial and ulnar arterial samples are usually preductal but can occasionally be postductal; umbilical arterial lines and posterior tibial lines (both sides) are always postductal.
 - e. in patients without arterial access, an OSI (oxygen saturation index) will be used
- (vii) Supplemental oxygen at 28 d, and 56 d (or discharge, whichever comes earlier) from the hospital – primary institution or secondary institution to which patient was transferred. The use of supplemental oxygen at 28 d will be used to calculate the incidence of chronic lung disease. Chronic lung disease severity will be classified similar to the BPD classification in preterm infants at > 32 week gestation (Jobe and Bancalari 2001). Intermittent supplemental oxygen given only during feedings or for spells administered for < 60 minutes and if the infant is not receiving oxygen at any other time during the day will not be considered as “supplemental oxygen”.

- a. Time point of assessment: 28 d, 56 d postnatal age or discharge to home whichever comes first.
- b. Mild CLD: treatment with oxygen > 21% oxygen for at least 28 days but breathing room air by 56 days' postnatal age or discharge to home whichever comes first.
- c. Moderate CLD: need for > 21% but < 30% oxygen at 56 days postnatal age or discharge to home whichever comes first.
- d. Severe CLD: need for \geq 30% oxygen and/or positive pressure (high-flow nasal cannula – defined for the purpose of this study as > 2 LPM, non-invasive ventilation or nasal intermittent positive pressure ventilation – NIV or NIPPV, CPAP, or positive pressure ventilation) at 56 days' postnatal age or discharge whichever comes first.

(viii) Survival to discharge (or day 120, whichever comes earlier) without ECMO and

(ix) Clinical status – pulmonary (use of supplemental oxygen or respiratory medications – pulmonary vasodilators (sildenafil, bosentan etc.,), diuretics, methylxanthines, steroids, inhaled or nebulized steroids or bronchodilators) and nutritional (weight, length, head circumference, use of anti-reflux and prokinetic medications) at discharge from the hospital and at 12 months of age. In addition, a review of clinical status will also be performed at 4 and 8 months of postnatal age.

(x) Feasibility to perform a definitive trial (primary outcome – improvement in survival without ECMO) and safety (incidence of systemic hypotension, intracranial bleeding and arrhythmias)

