Infusion of the study drug will be stopped if the mean blood pressure decreases < 35 mmHg and by > 20 mmHg (from pre-study drug mean blood pressure) after initiation of study drug and remains low for 2 hours despite treatment with > 40 ml/kg/24h of fluids and vasoactive medications (with a vasoactive inotrope score of > 30). Once the study drug is discontinued for improvement in oxygenation or a decrease in systemic blood pressure, it will not be restarted even if the condition leading to discontinuation changes (such as change in oxygenation or blood pressure). However, clinical providers can initiate open-label milrinone at their discretion. Study drug will also be stopped in the presence of renal dysfunction and/or development of a large intracranial (intraventricular with distension of the ventricle or parenchymal) bleed/echodensity.

Primary Outcome:

The primary outcome is the oxygenation response, as determined by change in OI (or OSI if no arterial blood gas is available) at 24h after initiation of study drug. In patients that require ECMO or die prior to completion of 24h from the initiation of the study drug, the last OI (or OSI if no arterial blood gas is available) prior to initiation of ECMO or death will be used for analysis. In patients without an arterial line (or if the line is lost), oxygen saturation index (OSI) will be calculated using a preductal oximeter. (Rawat, Chandrasekharan et al. 2015)

Secondary outcomes:

- (i) Oxygenation response at 24 h after initiation of study drug assigning a minimum OI of 40 or OSI of 20 for subjects that need ECMO or die after initiation of study drug infusion but prior to 24h of study-drug infusion. In this analysis if the patient's OI is 30 (or OSI of 15) and is cannulated for ECMO due to hemodynamic instability, he/she will be assigned an OI of 40 (or OSI of 20). However, if the OI prior to ECMO is 47 (i.e., > 40), the higher number (47) will be used for analysis of this secondary outcome.
- (ii) Oxygenation index at 48 and 72 h after initiation of study drug (or OI/OSI at the time of initiation of ECMO or immediately prior to death, for infants placed on ECMO or died before these time points),

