4.1.1. Inclusion Criteria

Infants are eligible if they meet all of the following criteria:

- (i) ≥ 36 0/7 weeks PMA by best obstetric estimate AND birth weight of ≥ 2000 g
- (ii) postnatal age ≤ 7 days (168 hours of age), including post-operative infants following CDH repair with HRF within this postnatal age,
- (iii) invasive mechanical ventilation (defined as ventilation with an endotracheal tube) and
- (iv) one arterial blood gas with an OI ≥ 10 (after tracheal tube obstruction, pneumothorax and other easily resolvable mechanical causes for increased OI are ruled out) on the most recent arterial blood gas within 12 hours prior to the time of randomization.
- (v) if an arterial blood gas is not available at the time of randomization, a preductal OSI of ≥ 5 can be used as an inclusion criterion instead of OI ≥ 10 ; (the OSI should be based on the most recent preductal pulse oximetry recording and must be within 12 hours of randomization)
- (vi) postnatal blood gas with $\text{PCO}_2 \leq 80$ mmHg (arterial, capillary or venous blood gas) on the most recent blood gas sample obtained within 12 hours prior to randomization

Note: Criteria (iv) to (vi) must be met at the most recent analysis within 12 hours prior to randomization.

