4.2. DETAILED STUDY PROCEDURES

For the purpose of the study, time period prior to study drug is defined as 12 hours prior to initiation to 30 minutes prior to initiation of study drug. Baseline is defined as the period 30 min prior to initiation of study drug. The monitoring period is defined as the period of study drug infusion and the first 24-hours following study drug cessation.

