(b) The study is also not powered to compare a sicker cohort of CDH patients similar to that evaluated in the CDH NINOs study (1997). The patients in CDH NINOs study had an OI of approximately 45 with standard deviations of 16.3 and 14.5 in control and treatment groups respectively. Such a cohort will require a sample size of 207 patients in each arm to achieve the primary outcome outlines in the current protocol. We intend to enroll patients early at a lower OI (or OSI).

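### Secondary outcome (i): the OI 40 floor ignores baseline, so an infant who fails from a baseline above 40 after a fall in OI is scored as improved

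*Combined protocol and SAP*

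**What the plan says.** Section 3.2(i), repeated in the protocol summary, defines a 24 h oxygenation response with a special rule for infants who go on ECMO or die before 24 h: "assigning a minimum OI of 40 or OSI of 20". Two worked examples fix its meaning. A last OI of 30 is raised to 40. A last OI of 47 is left alone: "the higher number (47) will be used for analysis of this secondary outcome". The floor is a minimum, not a constant, and neither example mentions the infant's starting value.

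The scale comes from Section 3.1: "The primary outcome is the oxygenation response, as determined by change in OI". Section 5.4 analyses the primary outcome as the difference from baseline OI in a linear model adjusted for HRF severity, and says that other continuous outcomes are handled in the same way. Section 4.2 fixes the reference point: "Baseline is defined as the period 30 min prior to initiation of study drug".

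Section 4.1.1 sets a lower OI limit of 10 for entry and no upper limit. Section 4.1.2 excludes infants on ECMO or actively considered for it, without an OI cut-off.

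**The concern.** The primary outcome takes the last OI before ECMO or death as it stands, so an early failure carries no penalty there. Outcome (i) is the only 24 h oxygenation analysis that adds one. A penalised score should not come out as a benefit, but because the floor is not tied to baseline, it does so for some infants whose baseline is above 40.

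Failure with a falling OI is not far-fetched under this protocol. Its own example is an infant cannulated at OI 30 for hemodynamic instability, and the general ECMO guidelines in Section 4.2.5 include hypotension and metabolic acidosis. Section 3.5 names systemic hypotension as a risk of milrinone. An infant whose oxygenation improves while the circulation fails is one that outcome (i) should not credit with improvement.

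**Working it through.** **The plan's own figure.** Outcome (i) has no stated power or sample size. The only stated figure nearby is the 84% power in Section 5.1 for the primary outcome (33 per arm, difference 4.6, SD 6.2, two-sided alpha 0.05). A two-sample t-test calculation gives 84.3%, so it reproduces. Nothing below alters it.

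**Inputs**
- Assigned value A = max(40, last OI), or max(20, last OSI) (Section 3.2(i)).
- Score = A − baseline (Sections 3.1 and 4.2).
- Entry OI at least 10, no upper limit (Section 4.1.1).
- 33 infants per arm (Section 5.1).

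**When is the score negative?** max(40, last) − baseline < 0 requires both baseline > 40 and last < baseline. For OSI, replace 40 by 20.

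| Index | Baseline | Last value | Assigned now | Score now | Score with baseline in the maximum |
|---|---|---|---|---|---|
| OI | 25 | 30 | 40 | +15 | +15 |
| OI | 40 | 30 | 40 | 0 | 0 |
| OI | 45 | 30 | 40 | −5 | 0 |
| OI | 46 | 38 | 40 | −6 | 0 |
| OI | 50 | 42 | 42 | −8 | 0 |
| OI | 55 | 30 | 40 | −15 | 0 |
| OI | 50 | 55 | 55 | +5 | +5 |
| OSI | 24 | 15 | 20 | −4 | 0 |

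The first two rows and the +5 row show where the present rule behaves as intended: baselines at or below 40, and infants who worsen from above 40.

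**Can baseline exceed 40?** Yes. There is no upper entry limit. The entry gas may be up to 12 h old at randomization and study drug may start up to 5 h later, while baseline is the last 30 min before the drug, so an infant may enter lower and pass 40 in between. OI of at least 40 for 3 h is only a general ECMO guideline, and the decision is left to the clinical team.

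**Size, as an illustration.** Shift in an arm mean from one such infant scored d instead of 0 = d/33:
- d = −5: −5/33 = −0.15
- d = −10: −10/33 = −0.30
- d = −15: −15/33 = −0.45

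The between-arm difference of interest is 4 points in Section 3.1 and 4.6 in Section 5.1.

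**The case against.** The strongest reply is that this is an edge case. Infants actively considered for ECMO are excluded, and the ECMO guideline starts at OI 40, so many infants above 40 would be screened out. Section 5.1 mentions a baseline near 45 ("The patients in CDH NINOs study had an OI of approximately 45") only to describe a sicker cohort for which this trial is not powered, and states an intent to enrol early at lower OI. All of this stands: it makes the case less common, but does not rule it out.

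Three stronger readings are tempting and are not supported.

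- *That the rule gives the wrong sign for the sickest infants in general.* It does so only if the last OI is below baseline. Higher observed values are kept, so worsening from above 40 is scored as worsening.
- *That outcome (i) is the only protection against hidden ECMO and death.* Outcome (viii), survival without ECMO, captures both, and Section 5.4 plans Cox models for survival without ECMO.
- *That the bias can be sized from Table 6.* Infants there with OI of at least 10 who had ECMO or died had OI 35, SD 19. Depending on the assumed distribution, 30% to 44% of that group lie above 40. But those are values 6 h after admission in infants who failed at any time before discharge, without this trial's exclusions. The table gives neither failure within 24 h nor the direction of OI change. Supposing two or three such infants per arm at −6 to −8 gives one-arm shifts of 2 × 6/33 = 0.36 to 3 × 8/33 = 0.73, but no source supports that count. If both arms have such infants the shifts largely cancel: within that range the net effect is at most (24 − 12)/33 = 0.36, and it may be zero.

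**Conclusion.** The point holds in a narrow form. As written, outcome (i) scores an infant who needs ECMO or dies before 24 h as improved when baseline OI is above 40 (OSI above 20) and the last value is below baseline. No other section prevents this. It rests on reading the oxygenation response in outcome (i) as a change from baseline, which is how Section 3.1 defines the term.

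How often it will happen cannot be taken from the documents. The 0.15 to 0.45 points per infant is an illustration that assumes scores of −5 to −15 and a full arm of 33. The effect is small against 4 to 4.6 points and confined to one secondary outcome; the primary outcome and the sample size do not change. It is still worth correcting, because the score has the wrong sign in the one 24 h oxygenation analysis that penalises early failure.

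**What to change.** In Section 3.2(i) and the matching item of the protocol summary, define the assigned value as the largest of 40, the baseline OI and the last OI before ECMO or death; for OSI, the largest of 20, the baseline OSI and the last OSI. No failure can then score below zero change. Scores at baselines of 40 or below, and for infants who worsen from above 40, stay as they are.

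The cost is one sentence in two places, using values already collected. It should be made before unblinding, since a later change to the scoring of failures would look data-driven.

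A worst-rank assignment should not be described as equivalent. Under the rule above, a failure with baseline 50 and last 42 scores 0 and ranks better than a survivor at +5, whereas worst-rank places every failure below every survivor. Section 5.4 also plans a linear model, not a rank test.
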